## A. Timeline for Randomized Control Trial (RCT)

Timelines	Activity/Task
Jun 15	All recruitment materials finalized and signed off
Jun 15	Final copies of all advertising materials, surveys and study instruments to be submitted to IRB
Jul 1-Aug 1	Recruitment
Jun 28	Refresher training of SPs; Staff training for the assessment
Jul 7-Sep 26	Completion of baseline assessment (baseline survey and SP) for intervention and control conditions
Sept 27-Oct 1 and Oct 3- 6	Dates of the training (Intervention only)
Oct 4	Day to make up training in case of emergency (intervention only)
Nov	Revision and finalization of protocol for the final assessment.
Dec	3-month follow-up surveys for both intervention and control Follow-up SP evaluations. (Project Coordinator will add date in once MUHAS Almanac is published in September).
Sept 2022	Intervention is run for the control group participants

## C. Study Participants

**1. Inclusion criteria:** A set of standards will be used to determine which students are eligible to participate in the September 2021 randomized controlled trial (RCT):

A health student studying at MUHAS (as verified by being registered in one of the following classes):

- a. Year 2 and 3 nursing students (the final year but one or two where students have significant community and Clinical experience).
- b. Year 2 and 3 midwifery students (the final year but one or two where students have significant community and clinical experience).
- c. Year 3 and 4 medical students (the final year but one or two where students have significant community and clinical experience).
- d. Able to speak English and Swahili. Because the education seminars are in English, but history talks are in Swahili. Therefore all students must be able to understand and converse in English and Swahili.

**2. Exclusion criteria.** Students who meet the eligibility requirements above will be excluded from enrolling and participating in the RCT if::

- a. Students who will not be able to attend MUHAS on all days of the seminar
- b. If they are not available during the follow-up assessment dates.
- c. Students who express any reservations about attending (e.g., due to religious objections)
- d. Students who show fear of violence due to attending (e.g., from a spouse or relative).
- e. Students who are physically unwell during the RCT.
- f. Students who have a body temperature greater than 37.5 C.

**Procedure:** All enrollees are logged at enrollment with their name, student ID and contact details. If a student meets any of the exclusion criteria, their student ID and the reason why they were excluded will be logged.

**3. Number of participants to be enrolled for the RCT.** There will be 422 students enrolled for the September 2021 full trial: 412 of whom will be participants in the trial, plus 10 extra medical students to be waitlisted in case of absences.

- a. 284 medical students (which includes 274 confirmed participants and 10 waitlisted enrollees). Of these, 137 will be randomized to the control arm and 137 to the intervention.
- b. 103 nursing students. Of these, 52 will be randomized to the control arm and 51 to the intervention.
- c. 35 midwifery students. Of these, 18 will be randomized to the control arm and 17 to the intervention.

**Back-up plan:** If there are insufficient students using these inclusion criteria, **Project Coordinator** may extend the invitation to be in the study to Year 3 midwifery, then Year 3 nursing, and then Year 4 medical students as well (on an “as space available” basis).

**4. Process for recruiting student participants and how to increase student participation for the full trial.**

The **Project Coordinator** in Dar es Salaam, TZ, will enroll 422 students (412 participants and 10 extra waitlisted enrollees) participants. WhatsApp, flyers, and advertising on notice boards methods, will be

used to recruit students (**see appendix F**). Recruitment will begin on **July 1** and continue until all participants and waitlisted enrollees are recruited.

**Research Assistant** is in charge of designing advertisements and posters. Deadline for signoff on all advertising is **June 25, 2021**. Advertisements and posters, once approved, need to be printed by **June 30, 2021**.

**Researcher 1** will notify student leaders and ask them to post the adverts in the student WhatsApp chats.

**Principal Investigator** is responsible for liaising with the medical school to inform them about the study and to ensure institutional buy-in and support.

**The leadership team** will receive weekly email updates from **Project Coordinator** starting on July 10 and be available to problem solve any difficulties in recruitment.

**5. Enrollment:** To enroll in the study, interested students will be informed on the posters, recruitment materials and in class announcements to call the study phone number or to visit the study office. **Study staff** will have each interested student complete a form detailing the name, phone number, MUHAS student ID, whether the phone number can receive texts, email address, type of student (midwifery, nursing, medicine), year of study, and date of enrollment. The staff will confirm eligibility and exclusion criteria as detailed above. Each student's information will be entered into a database with preferred contact information. Either when the student enrolls, or when the study staff contact her to confirm enrollment, the study staff will give them a day (and approximate time) to come to MUHAS to complete the baseline study activities. They will also inform them to bring their phone or other device to complete an online survey when they come to their baseline appointment.

**6. Recruitment timeline:** Recruitment should be completed at least one week before the start of the trial (i.e. by Friday, September 17). **Project Coordinator** will confirm with all participants three days prior to the first day of baseline measures. Waitlisted persons will be asked to complete the baseline measures and SP, be paid for doing so, and to provide a cell phone number to be contacted in case of no shows on Day 1.

**7. Confidential list of participants.** This list will be kept in a locked file cabinet. Only **Project Coordinator** and **Principal Investigator** will have a key to the cabinet. **Project Coordinator** will also download a copy onto the external hard drive and store it in a different location.

All electronic information containing names and/or student ID numbers shall only be saved behind electronically protected password firewalls.

**8. Attendance at the Seminar by Non-participants.** For ethical reasons, in the grant we have said that students who do not want to participate in the research but do want to attend the training can do so on a space available basis. Given the COVID requirements for spacing, all such students will be informed they may attend the training in **September 2022**, but that only research participants and study faculty can attend in 2021. Similarly, this training is closed to other faculty. Only study staff, the trainers and the participants should be allowed inside the lecture theater.

## **9. Randomization of Participants to Study Arms**

**Objective:** The purpose of the randomization is to assign students to the intervention or control group arms of the trial in a way that is fair and is seen by the participants to be fair. It is also done to prevent students from trying to change their assignment from one group to the other.

We will use a block randomization for each group (midwifery, nursing and medical students), batch (in groups of ten) randomization process. Once students have completed the baseline SP and survey, they will receive their assignment in an envelope.

For logistical reasons, the students are randomized after undertaking the baseline assessment. To prevent several threats to study validity, the students and staff should not be told a student's assignment to the intervention arm or the control arm until after they have completed the baseline assessment.

- a. **Researcher 2 and Researcher 3** are in charge of the randomization.
- b. **Researcher 3** will keep three envelopes titled "midwifery", "nursing", and "medical student" envelopes. Inside these envelopes at the start of each cycle are 10 pieces of paper, all the same size. Five pieces of paper will have the word "2021" on them and five will have "2022."
- c. **Researcher 3** draws a piece of paper with 2021 on it, they will record the student who will be attending the training in 2021 (i.e., next week). If s/he draws a piece of paper with 2022 on it, they will be recording the student as eligible to attend the training in 2022.
- d. **Batch Randomization:** Once a piece of paper is drawn, it is NOT returned to the envelope but instead put in the "used envelope" for reuse later. So, when the first medical student is to be randomized, **Researcher 3** draws from the medical students' envelope with 10 pieces of paper in it; for the second, they draw from the envelope which now has 9 pieces of paper in it, and so forth. When the envelope has no more pieces of paper left in it, the envelope is refilled so it has 5 2021 and 5 2022 pieces of paper.
- e. **Researcher 3** then records the randomization on a master list of students.
- f. **Note:** Staff involved in the randomization should avoid using the terms "intervention" and "control" groups. Instead, we use the term, the training happening next week or the training for next year.
- g. Students cannot trade their place in the training with another student. This is to avoid bias such as more committed students ending up in the intervention arm.
- h. Note: Students who enroll as a "waitlist" student (i.e., the 7 students who enroll after the category is filled) complete the baseline assessment but are not required to be randomized. (This is because they will be assigned to the intervention if another student cannot make it).

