So, [name] is say, 09. When [name] is acting for Case Study B. the number is 509. But if [name] also works on Case study D, that would be 709.

- d. Treatment arm: [THIS INFORMATION IS DELIBERATELY NOT IN THE SOP SO THAT THE TEAM MEMBERS AT MUHAS EVALUATING THE SP VIDEOS REMAIN BLIND TO THE CODE. THE CODE IS TWO NUMBERS BETWEEN 20 AND 79 GENERATED BY METHODOLOGIST. SHE WILL SEND THESE NUMBERS TO PROJECT COORDINATOR WITH THE INSTRUCTION TO USE THEM WITH THE PARTICIPANTS AT BASELINE. AT FOLLOW-UP METHODOLOGIST WILL SEND ANOTHER SET OF NUMBERS, ALSO BETWEEN 20 AND 79 FOR USE ONLY AT FOLLOW-UP. METHODOLOGIST WILL RETAIN THE KEY TO INTERPRETING THESE DIFFERENT NUMBERS].
- e. Expert raters are assigned a number that mirrors the SPs, starting at 51-60
  - i. Expert Rater Case study A – 451-460 (one for each rater)
  - ii. Expert Rater Case study B – 551-560
  - iii. Expert Rater Case study C – 651-660
  - iv. Expert Rater Case study D – 751-760

So, **Researcher 2** is assigned a unique number, say, 55. When **Researcher 2** is evaluating Case Study B, she assigned each case 555. But if **Researcher 2** also evaluated Case Study C, she would use the number 655.

Examples:

So, the study number appearing on a survey may look like this:

671423 – 02 – 300 – 54

Student ID# – Midwifery student – follow-up survey – Intervention arm

451207 – 03 – 100 – 27

Student ID# – Nursing student – baseline survey – Control arm

671523 – 01 – 200 – 54

Student ID# – Med student – post-test survey – Intervention arm

So, the study number appearing on an SP rater form may look like this:

671523 – 01 – 401 – 54

Student ID# – Med student – Case Study A (John SP) – Intervention arm

671423 – 02 – 603 – 54

Student ID# – Midwifery student – Case Study C (Sara SP) – Intervention arm

451207 – 03 – 502 – 27

Student ID# – Nursing student – Case Study B (Mary SP) – Control arm

The number on the expert rating form will look like this

451207 – 03 – 502 – 27 – 553

Student ID# – Nurse – Case Study B (Mary SP) – Control arm – **Dr. X** rater

671423 – 02 – 402 – 54 – 455

Student ID# – Nurse – Case Study A (John SP) – Intervention arm – **Researcher 2** rater

671523 – 01 – 702 – 54 – 753

Student ID# – Nurse – Case Study D (John SP) – Intervention arm – **Dr. X** rater

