### Procedures for administering the survey

- a. **Researcher 3** is in charge of overseeing the baseline survey completion.
- b. Each participant is instructed to complete the online using their phone, laptop, or other online devices.
- c. The survey will be completed online using a Qualtrics survey.
- d. As a backup plan, 100 surveys will be printed on paper, to be distributed to any student who does not have access online and/or if the Internet goes down.
- e. **Researcher 3** will ensure she has enough surveys, along with **pens and pencils**.
- f. If more surveys are needed they can be printed while the first 100 are being used.
- g. **Researcher 3** will inform each participant as she hands them the survey, to ask her if they have any questions.
- h. For online surveys, once the student completes the survey the responses will be saved automatically in the Qualtrics database. **Project Coordinator** will monitor the database and make sure that all survey data has been recorded.
- i. For paper surveys, **Researcher 3** is responsible for collecting them and handing them to Project Coordinator at the end of each day.
- j. [name] will address any participant concerns. Should a student be in a hurry and asks if they can complete the online survey on their phone later, [name] may allow them to do so. But she will tell the participant they will not receive any payment or be randomized to the intervention or control until they complete the online survey.
- k. Each student is informed to return to **Researcher 3** when they have completed the baseline survey. **Researcher 3** will check if they have completed the survey online, that they have reached the last page. For any participant who completes the pen and paper survey, **Researcher 3** will collect the form, while the student is in front of her, she will quickly check that no pages have been skipped and if the form is completed, thank the student.
- l. She instructs the participant that they have completed the baseline survey and should go next to the randomization table.

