## 6. Informing the students about their randomization to the seminar in 2021 or 2022.

- a. Once the student has completed the baseline assessment, they return to the final table.
- b. **Project Coordinator** will ask each participant whether s/he has signed their consent form, completed two SP scenarios and rated themselves on two SP forms, and completed the baseline survey.
- c. For students who say yes to all questions, **Project Coordinator** then consults the master list to see if the student is assigned to attend the seminar in 2021 or 2022.
- d. For students assigned to 2021, **Project Coordinator** hands the student the one-page flyer providing the student with all the information about the seminar including the dates, times, and location of the seminar, that the student is expected to attend all days, the need to wear a mask and other COVID precautions in place, that the student will be expected to attend all four days of the seminar, the amount per day and the total amount of compensation and that the student will only be compensated for each day they attend the seminar, that the student cannot trade their place in the seminar with another student, the cell phone to call in case of problems, and any

other information. This flyer will also ask students not to share information on the baseline assessment with other students, and not to share information or content from the training with students who are not at the training. For ethical reasons, this flyer will have a sentence noting that participation in the research study is voluntary and that the student can withdraw from the study at any time. However, students will be compensated only for the tasks they complete such as filling in the surveys and attending the seminar. **Project Coordinator** will then ask if s/he has any questions and answer them. And then he will ask the student to confirm their intention to attend the seminar.

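### One researcher keeps, draws and records slips from known 5:5 blocks of ten and also passes students on to the draw, so about one assignment in six is certain in advance and no independent record of the draw is specified

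*Protocol*

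**What the plan says.** Protocol Section C.9 describes a "batch (in groups of ten) randomization process" carried out separately for midwifery, nursing and medical students. Researchers 2 and 3 are jointly in charge, but every listed task falls to Researcher 3, who "will keep three envelopes titled" for the three disciplines, draws each slip, and enters the result on the master list (items b to e). Each cycle starts with five slips for 2021 and five for 2022. A drawn slip goes into a second envelope to be used again, and "When the envelope has no more pieces of paper left in it, the envelope is refilled". The slips are described only as equal in size. No pre-generated sequence, witness, numbering or timed log of draws is mentioned.

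In Section G.5, Researcher 3 also "is in charge of overseeing the baseline survey completion" (item a), checks that the student has finished (item k), and directs the student to the randomization table (item l). In Section G.6 the Project Coordinator asks the student about consent, the two simulated-patient cases and the survey, and "then consults the master list to see if the student is assigned to attend the seminar in 2021 or 2022".

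C.9 places the draw after the baseline assessment. Item g forbids trading places, so that more committed students do not collect in the intervention arm.

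**The concern.** Concealment requires that whoever decides a student is ready cannot know or influence the next assignment. Here one role holds the remaining slips, knows where each block begins and ends, makes the draw, writes the only described record of it, and controls the last baseline step before it.

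Two routes to bias stay open. The order in which waiting students of one discipline are drawn could be steered when the next slip is known or likely. A slip could also be put back and another drawn. Either could move keener students into the 2021 arm, which is the bias C.9 item g tries to exclude. The SAP would not adjust it away: its model of change scores contains intervention, discipline, gender and religion, and none of these measures commitment.

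**Working it through.** **Inputs.** From C.9: blocks of 10, five slips per arm (m = 5), no replacement, refill only when empty. From C.3: 274 medical, 103 nursing and 35 midwifery students to be randomized. Assumption: the observer keeps a running tally within each discipline, as the holder of the envelopes can.

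**The plan's own total.** 274 + 103 + 35 = 412, made up of 137 + 52 + 18 = 207 control and 137 + 51 + 17 = 205 intervention. The stated 412 is reproduced.

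**Assignments certain before the draw.** A draw is certain when all r remaining slips are alike, with probability 2 × C(10 − r, 5) / C(10, 5), where C(10, 5) = 252.

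| Position in block | r | Probability certain |
|---|---|---|
| 1st to 5th | 10 to 6 | 0 |
| 6th | 5 | 2/252 = 0.8% |
| 7th | 4 | 12/252 = 4.8% |
| 8th | 3 | 42/252 = 16.7% |
| 9th | 2 | 112/252 = 44.4% |
| 10th | 1 | 252/252 = 100% |

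The sum is 420/252 = 1.67 per block, which agrees with the closed form 2m/(m + 1) = 10/6.

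**Correct guesses.** Always guessing the arm with more slips left gives m + ½ × (2^(2m)/C(2m, m) − 1) = 5 + ½ × (1024/252 − 1) = 6.53 per block of 10, or 65.3%, against 50% by chance. Full enumeration of the 252 orderings gives the same two values.

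**Whole trial.** Complete blocks: 27 medical + 10 nursing + 3 midwifery = 40, with part-blocks of 4, 3 and 5.
- Certain: 40 × 1.67 = 66.7. The part-blocks add none, because they stop at or before the fifth draw. That is about 67 of 412 (16%).
- Guessed correctly: 40 × 6.53 = 261.3. The position-by-position rates 0.500, 0.556, 0.556, 0.595 and 0.595 add 2.2 + 1.6 + 2.8 = 6.6 for the part-blocks. The total is about 268 of 412 (65%).

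**Comparison.** To someone who sees neither a pre-generated list nor the past assignments, no assignment is certain and the guess rate is 50%.

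**The case against.** The strongest defence is that the draw comes late and that several people stand around it. Students have consented and finished baseline before any slip is drawn, so knowing the next slip cannot change who enrolls. Study staff confirm eligibility at enrollment (C.5), the simulation-lab lead checks the simulated-patient forms (G.4), and the Project Coordinator makes the final check and releases the assignment (G.6). About five assignments in six are not certain. Steering also needs another student of the same discipline to be drawn first. All of this stands, and it limits the harm. It does not protect the draw itself: G.6 has the Coordinator read an assignment from the list and does not say whether the slip was drawn before or after that check.

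A reader might infer four stronger points that the documents do not support.

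- *The allocation cannot be audited at all.* A master list exists and other roles use it. If it keeps draw order, which is not stated, balance within each ten can be checked. What leaves no trace is an individual redraw or chosen slip.
- *Researcher 3 controls the order of entry.* G.5 item j says that students who finish late are told "they will not receive any payment or be randomized to the intervention or control until they complete the online survey". However, the person who may permit this is a removed name, and the student makes the request. Control of order by Researcher 3 is possible but not shown.
- *The arm codes in Section D require allocation before baseline ends.* The methodologist sends them with "THE INSTRUCTION TO USE THEM WITH THE PARTICIPANTS AT BASELINE", but the draw follows baseline directly and a code could be added then. The timing is unstated, not contradictory.
- *The exact splits printed in C.3 bear on concealment.* Blocks of ten do not guarantee them, since 274, 103 and 35 are not multiples of ten. That says nothing about whether assignments can be foreseen, and a difference of a student or two between arms causes no bias.

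**Conclusion.** The weakness is real and moderate. As written, keeping, drawing and recording lie with one role, Researcher 2 has no stated task, and that one role also passes students on from the survey. About one assignment in six is foreseeable with certainty and about 65% can be guessed, provided a tally is kept; both figures follow from the 5:5 block of ten and need no assumption about outcomes. No independent record would reveal a redraw.

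The documents do not show that any draw was steered, and they give no basis for estimating an effect on the outcomes. The conclusion concerns what the procedure permits, and it is worth acting on because better protection is inexpensive.

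**What to change.** Have the methodologist, who already generates the arm codes (Section D), prepare one list per discipline with randomly varying block sizes. Make each list slightly longer than needed and do not force it to end on the C.3 splits, because a forced ending makes the last assignments deducible. Restate those splits as approximate. Place the assignments in sequentially numbered, sealed, opaque envelopes. An existing staff member other than the survey overseer opens the next envelope only after baseline completion is logged, and records the sequence number and time.

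The cost is one preparation of lists and envelopes, a change of who opens them, loss of the simple hand draw, and slightly less exact arm totals.

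The SAP shows that the 412 have already been recruited. For this trial, what remains is to check the master list for draw order and balance within each ten, compare the arms at baseline, and report the allocation method as it was done. The new procedure applies to any later use of this design.

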**3. Anticipated challenges and how to address them**

1. **If a student arrives late or leaves early, what happens?** If a situation like this happens then the supervisor (**Project Coordinator**) will discuss with the students if she wishes to continue or not. The supervisor will weigh the reasons provided and the time frame then he will make decisions.
  - a. **Project Coordinator** is the person responsible for deciding who can enter the study or not. We anticipate two types of non-attendance:
  - b. **Group non-attendance.** If because of weather or some other event a significant portion of the participants cannot attend, then **Project Coordinator** shall decide whether to delay the start of the seminar and/or change the timetable to facilitate everyone's attendance.
  - c. **Individual non-attendance:**

- i. If an individual notifies the study that s/he cannot attend, then if it is on or before Day 1 of the seminar, Project Coordinator shall replace this participant with one of the waitlist participants.
- ii. If an individual arrives within an hour of the seminar starting, study staff will record the time of arrival, the student's ID number, and any reason given for lateness, before admitting them. Similarly, if a participant needs to leave up to an hour early, study staff will record the time of departure, student's ID, and any reason given for the early departure.
- iii. If an individual is more than an hour late or needs to leave more than an hour early, or requests being absent from the training for more than an hour, this shall be referred to **Project Coordinator**. They will decide whether to let the participant continue and whether the participant receives compensation for that day. (Note: We prefer students to continue receiving the training and, in the study, wherever possible).

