d. **Individual withdrawal from the Study.** This study is voluntary, therefore if anyone chooses to withdraw from the study, study staff will allow them to do so. Anyone notifying the study that intends to not attend the rest of the training shall be referred to **Project Coordinator**. **Project Coordinator** will review the intent of the participant and any reason why they will not be continuing in the training. Depending on the reason (e.g., sickness, family emergency, the decision to withdraw), he will thank them for informing the study of this decision, inform them that they will be compensated for the days attended but not days not attended, and will record the reason given why the participant dropped out of the study. Finally, **Project Coordinator** will ask if the participant is dropping out of the training only, or is wishing to drop out of the study. (NOTE: If a participant drops out of the training, they are still considered a participant and we prefer them to complete the post-seminar evaluation and the follow-up even if they missed part of the training).

2. **If a student misses a survey, what happens?** If a student is missing the baseline survey and/or the SP evaluation, he/she will not be allowed to participate in the training. Instead, his/her place will be given to one of the students on the waitlist.

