## 2. Minimization of Drop Out

- a. Participants in both arms of the trial are easily followed up since they are enrolled students at MUHAS. At enrollment, students will be asked to supply a mobile number to contact them in case they need to. Should a participating student not keep their pre-test or 3-month follow-up appointment, every effort will be made to facilitate another session for them to complete study tasks. Participant attendance at the seminar is monitored.
- b. If a participant leaves MUHAS and is no longer considered a student, they can remain a participant in the study and so can participate in the follow-up portion of the study. **Project Coordinator** is the staff person who shall discuss with the participant the reason why they are no longer a student and may include or exclude the student from further participation (as appropriate).
- c. **Project Coordinator** will keep a log of any students who inform the study that they wish to no longer participate. This study is voluntary so a participant may choose to leave the study at any time. **Project Coordinator** shall ask them for any reasons for withdrawal.
- d. Also, he will follow up with any participant who completed the baseline assessment but failed to complete the follow-up. Every effort will be made to facilitate the student completing the follow-up. Should he encounter participants who “disappear” from the study (i.e., they enrolled in the study and completed the baseline but then were not contactable for follow-up, he will check with MUHAS administration and the relevant school whether the participant is still a current student, and if not, the reason why. Given the COVID epidemic, he will log the reason given why the participant is no longer a student (e.g., illness or death at the time of follow-up).

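### Never-randomised waitlist students can take intervention places, and the SAP does not say that Intervention means the arm drawn (minor)

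*Protocol*

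**What the plan says.** **Replacement.** Randomisation follows the baseline assessment, by drawing slips from an envelope for each discipline (Protocol C.9). Waitlist students do the baseline but are not drawn; item h says "they will be assigned to the intervention if another student cannot make it". Under C.6 they leave a phone number "to be contacted in case of no shows on Day 1". Under H.3, when a student gives notice on or before Day 1 that they cannot attend, "Project Coordinator shall replace this participant with one of the waitlist participants".

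**A second route, which displaces nobody drawn.** For a student with a missing baseline survey or simulated-patient evaluation, H.3 item 2 says "Instead, his/her place will be given to one of the students on the waitlist". Section G.5 item j says such a student will not "be randomized to the intervention or control until they complete the online survey", and C.9 places the draw after the whole baseline. This route comes before allocation.

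**Who may enter.** Section D, item c, has staff check each student at the door against a list of those randomised to the intervention.

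**Displaced students.** C.2 excludes "Students who will not be able to attend MUHAS on all days of the seminar", and for excluded students "their student ID and the reason why they were excluded will be logged". H.3 item d keeps people who leave the training as participants. N.2 says of the Project Coordinator that "he will follow up with any participant who completed the baseline assessment but failed to complete the follow-up". N.4 item f still describes a student who could not attend as assigned to the intervention arm.

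**Analysis.** The SAP's primary predictor is a 0/1 Intervention indicator and the outcome is follow-up minus baseline. From 412 recruited, it removes one participant with no post-intervention survey and three with no follow-up. After the gender and religion exclusions it models 396. It does not mention the waitlist or replacements, or state that analysis is by arm drawn.

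**The concern.** A replacement enters the intervention arm because someone else was unavailable after allocation, and the replacement was never subject to the draw. If replacements are coded as intervention, or the students they displaced are left out, part of that arm is set by availability. Nothing similar happens among controls. C.9 item g bars students from swapping places precisely to avoid selection of this kind, and item h then opens another way in.

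The protocol also conflicts with itself. An undrawn replacement would not be on the door list in section D unless someone added them, so these passages must be reconciled. C.2 could be read as taking a non-attender out of the study, while H.3 item d, N.2 and N.4 item f keep non-attenders in it. Two analysts could therefore build different intervention arms from the same records, each with support in the text.

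The removal for a missing post-intervention survey is a related matter. Controls had no such survey, so the rule can remove people from one arm only, and it does so for a measurement that the change score does not need.

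**Working it through.** **Reproducing the planned numbers (C.3 and SAP).** Intervention: 137 + 51 + 17 = 205. Control: 137 + 52 + 18 = 207. Total 412, and 412 + 10 waitlisted = 422. SAP: 412 − 1 − 3 = 408; 408 − 396 = 12 removed on gender or religion; 396/412 = 96.1%, which agrees with the stated 96%.

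**Size of a possible shift.** Suppose k replacements are coded as intervention and the k replaced students are dropped. Let d be the difference in mean change score, in SD units, between replacement and replaced students, apart from any training effect. The intervention mean moves by (k/205) × d. The documents give no value for d, so 0.25, 0.5 and 1.0 are assumed; 1.0 is extreme.

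The standard error of the unadjusted arm difference is sqrt(1/205 + 1/207) = 0.0985 SD. Type I error is P(|Z + shift/0.0985| > 1.96). The 1.96 assumes a two-sided 0.05 test, which neither document states.

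| k | k/205 | Shift at d = 0.25, 0.5, 1.0 (SD) | Type I error |
|---|---|---|---|
| 7 (C.9 item h) | 3.4% | 0.009, 0.017, 0.034 | 0.051, 0.053, 0.064 |
| 10 (C.3) | 4.9% | 0.012, 0.024, 0.049 | 0.052, 0.057, 0.079 |

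At k = 10 and d = 0.5 the shift is 0.0244/0.0985 = 0.25 standard errors. These rows assume that every waitlist place was used, so they are upper bounds.

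**If the 412 are the students as drawn.** The post-intervention survey is completed in the room after training (H.2 item d), and one participant lacks it. If a non-attender would not have completed it (an assumption), at most one drawn student missed the training. Dropping that student moves the arm mean by d/205, where d is now the difference between retained and dropped students: 0.5/205 = 0.002 SD.

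**Effect of keeping the participant without the post-intervention survey.** If that participant has follow-up data, 412 − 3 = 409 replaces 408. The modelled set becomes at most 409 − 12 = 397, or stays at 396 if that participant also falls under the gender or religion exclusion.

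**Does an existing record settle the coding?** Two records bear on it. C.9 item e puts each draw on a master list. Section D, item e, puts a treatment-arm code in each study number, with one set of codes at baseline and another at follow-up, and the methodologist holds the key. Neither says what code a replacement receives, or whether a replaced student's code stands.

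**The case against.** The strongest reply is that the protocol already leans towards analysis as drawn. The arm code is attached at baseline, N.4 item f still calls a non-attender assigned to the intervention, and N.2 aims to follow up everyone with a baseline. The SAP's 412 most naturally matches the 412 participants in C.3, who are counted apart from the 10 waitlisted. This narrows the gap, and it would be wrong to say that the protocol keeps no record of arm. It does not close the gap: those passages do not cover replacements, and a roster that is still 412 after substitution is not excluded.

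Second, any effect is small. Change scores remove stable differences in level. The Nursing main effect adjusts for discipline where a medical waitlist student fills a nursing or midwifery place. This stands, and it is why the point is minor.

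Third, the SAP is dated December 2023 and already reports follow-up completion, so an exclusion rule written now comes after data collection. That also stands and has to be disclosed. It is not a reason to leave the predictor undefined.

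A reader might infer that randomisation was in fact broken, or that the result is biased. The documents do not support that: they report no replacement, and the sign of any shift is unknown.

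**Conclusion.** Minor. The replacement rule, followed as written, lets availability after the draw decide part of one arm, and the SAP does not say whether its primary predictor is the arm drawn. The removal for a missing post-intervention survey is likewise one-sided and not needed for the stated outcome. The plausible ceiling is the 0.5 SD case with every waitlist place used. Only the 1.0 SD assumption takes type I error to 0.079, and nothing in the documents suggests a difference that large. The case for acting rests on an undefined predictor that is cheap to define, not on a demonstrated bias. If the master list shows no replacements, a short statement closes that part, leaving only the removal for the missing survey to correct.

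**What to change.** Add to the SAP:

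- Intervention is the arm drawn, checked against the master list (C.9 item e) and the arm code (section D, item e). First confirm that draws on the list can be told apart from later additions.
- Drawn students with baseline and follow-up data stay in their drawn arm, whether or not they attended or completed the post-intervention survey. Recount the 408 and 396 accordingly.
- Replacements who were never randomised are left out of the primary analysis. An as-attended analysis is sensitivity only.
- Report the number of replacements, and of replaced students with and without follow-up data. State whether the 412 are counted as drawn or after substitution.
- State that the rule was added after data collection.

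Reconcile C.9 item h and H.3 with the door check in section D. As an editorial matter, reconcile the waitlist counts of 7 (C.9 item h) and 10 (C.3).

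**Cost.** A few sentences, a check of the list and a recount. If replaced students have follow-up data but gained nothing, the estimated effect is multiplied by at worst 195/205 = 0.951, a dilution of at most 4.9%. If they have no follow-up data, the standard error rises from 0.0985 to at most sqrt(1/195 + 1/207) = 0.0998 SD. In that case the one-sided exclusion remains, with a bias of the same form, (k/205) times the difference between retained and replaced students. No coding rule removes it, and it should be stated as a limitation.
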